## 13.7 Health Economic Analysis Plan

A full economic analysis plan (EAP) will be written prior to the conduct of any comparative analysis of the treatment arms. The main features of the EAP are summarised below:

Participants will be included in the analysis set based on the intention-to-treat principle.

Resource related to dental treatments will be taken from routine administrative claims data for the 24 months of the trial and subsequently for the 10 year follow-up. Treatments will be measured and monetised using the statement of dental remuneration for those delivered in the community and standard references for those delivered in secondary care. Where missing data exists multiple imputation methods will be used to estimate missing values. Intervention costs will be added to treatment costs for the intervention group.

Resource use and costs will be reported for the intervention and control groups at 24 months and 10 years using mean, median and standard deviations. Outcomes will be similarly reported at 24 months and for selected outcomes at 10 years. Differences in mean cost and outcomes between groups will be estimated and reported using t-tests. Differences in cumulative care costs over 24 months will be related to differences in effects as cost-effectiveness ratios following a bootstrapping exercise to take account of potential joint distributions between costs and outcomes. Sub-group analysis related to socio-economic status and ethnicity will be explored based on partitioned samples. Seemingly unrelated regression analyses will be used as an adjunct to the bootstrapping exercise and covariates for socio-economic status and ethnicity entered as covariates.

Sensitivity analysis, to include variation in specific elements of cost – for example based on the time and motion study of intervention delivery time – will be undertaken as will a probabilistic sensitivity analysis.

To take account of potential spill-overs related to sibling use of services, routine administrative data on dental service use by siblings aged <11 at the time of the study child's recruitment will be secured. Their use of services will be used to estimate spill-over costs and their outcomes measured or where unobserved estimated based on relationships between costs and outcomes for study children. Spill-over costs and outcomes will be added to those of the study child in sensitivity analysis at 24 months and 10 years.

Cost-effectiveness acceptability curves will be used to assess the value of the intervention assuming a variety of societal willingness to pay levels with respect to each outcome.

Data will be sourced from external organisations as described in the below flow chart:

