### 10.8.8 Health Economic Assessments

Utilization of care will be taken from clinical records and monetised using the Northern Ireland Statement of Dental Remuneration for care provided by the GDP and from National Cost Collections for hospital provided extractions. These costs will be aggregated over the 24-month study period in the base case analysis (and over 10 years in the follow-up study). To these will be added the cost of the intervention for the intervention group. Intervention costs will be based on nurse delivery time as recorded by the providing nurse and monetised using agenda for change pay rates for a dental nurse at band 2 in the base case analysis. As a validation exercise a random sample of intervention delivery times will be timed by the research team and compared with those reported by nurse providers. Incremental costs in the base case analysis will be based on differences in costs over 24 months between the control and intervention group. As a range of outcomes are captured in the study including the proportion who accumulate additional caries, the number of fillings provided, episodes of pain and quality of life (QOL) measures, a range of incremental effects will also be calculated based on differences in these at 24 months. Where appropriate, for example in respect of quality of life, incremental effects will be based on differences in the change in QOL between baseline and follow-up between intervention and control groups.

Mean differences in cumulative discounted costs and effects between the intervention and control groups will be described and tested using standard parametric approaches to examine differences in mean costs, proportion of children whose caries progress, episodes of pain, fillings and health-related quality of life etc. A series of incremental

cost effectiveness ratios will be estimated detailing the difference in cost divided by the difference in effect between intervention and control groups. To take account of the possibility that costs, and effects are jointly distributed, uncertainty around ICERs will be explored in deterministic models using a nonparametric bootstrapping approach and uncertainty around the willingness to pay for outcomes using cost effectiveness acceptability curves.

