A discount rate of 1.5% will be used in the base case analysis based on the intervention being construed to be a public health intervention. Missing data will be imputed using multiple imputation methods. An intention to treat approach will be adopted for analyses. Given observed disparities in oral health and use of dental services related to socio-economic status (SES) we plan to undertake sub-group analysis related to socio-economic status and ethnicity. Should significant differences in cost-effectiveness exist, the samples will be re-weighted to adjust for differences in SES and incremental cost-effectiveness re-estimated. As an additional check, a seemingly unrelated regression approach will be used to estimate ICERs and models adjusted and unadjusted for SES reported. This approach will be repeated with respect to ethnicity.

A series of sensitivity analyses will be undertaken. Individual parameter values will be varied in a series on one way sensitivity analyses that include unit costs, discount rates and time taken to deliver the intervention. Spill-over effects related to sibling effects will be added to those experienced by the index based on observed differences in use of dental care and the relationships between use of dental care and QOL observed from the literature and observed in the study. (How for example QOL varies with additional fillings and extractions,) A probabilistic sensitivity analysis will be used to examine the sensitivity of results to joint variations in input parameters.

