# 13.3 Method of Randomisation

### 13.3.1 Allocation Sequence Generation

Participants will be equally randomised to the intervention or control group in a 1:1 ratio using a secure (24-hour) web-based randomisation program controlled centrally by LCTC. Randomisation lists will be generated using block randomisation with random variable block length, stratified by site and age. The lists will be produced by an independent statistician (who is not otherwise involved in the CHOICE trial) at LCTC.

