## 13.6 Analysis Plan

A full statistical analysis plan (SAP) will be written prior to the conduct of any comparative analysis of the treatment arms. The main features of the SAP are summarised below:

Participants will be included in the analysis set based on the intention-to-treat principle.

The primary outcome will be compared between groups using logistic regression, adjusted for site and baseline dental caries.

Count outcomes such as number of teeth developing caries, number of fillings and number of extractions will be compared using Poisson regression adjusted for site and baseline caries. Secondary parent reported outcomes will be analysed using linear or logistic regression, adjusted for site and baseline values.

The comparative outcomes in different ethnic groups will be explored by adding terms for ethnicity and interaction terms between ethnicity and treatment to the models of caries and oral health behaviour outcomes. This will be an exploratory analysis as we have not powered the trial to detect interactions.

An exploratory analysis will be carried out to investigate the potential mediating effects of parental self-efficacy and relief/regret on the effect of the intervention on the clinical outcome. This analysis will test for partial mediation using a series of regression analyses. We will conclude that mediation is present if the four statements below are true:

- 1. The total of effect of DR-BNI on caries is significant
- 2. The effect of DR-BNI on the mediating variable is significant
- 3. The effect of the mediating variable on caries, adjusted for DR-BNI is significant
- 4. The direct of effect of DR-BNI on caries adjusted for the mediating variable is reduced from the effect modelled in step 1.

As much information as possible will be collected about the reasons for missing outcome data; this will be used to inform any imputation approaches employed in the analysis. Such methods will be fully described in the SAP.

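### The economic analysis estimates incremental cost and effect without adjustment and does not name baseline caries, site or age as covariates, which may cost precision

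*Protocol*

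**What the plan says.** Section 13.7, giving the main features of the economic plan: "Differences in mean cost and outcomes between groups will be estimated and reported using t-tests". The ratios are then formed: "Differences in cumulative care costs over 24 months will be related to differences in effects as cost-effectiveness ratios following a bootstrapping exercise". Seemingly unrelated regression is described there as an adjunct to the bootstrap, with "covariates for socio-economic status and ethnicity entered as covariates".

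Section 10.8.8 matches: "Mean differences in cumulative discounted costs and effects between the intervention and control groups will be described and tested using standard parametric approaches". It lists the outcomes that supply incremental effects, "including the proportion who accumulate additional caries, the number of fillings provided, episodes of pain and quality of life (QOL) measures". It treats the regression as an extra check: "a seemingly unrelated regression approach will be used to estimate ICERs and models adjusted and unadjusted for SES reported", with the same repeated for ethnicity. The only baseline handling mentioned is a change score where appropriate, with quality of life as the example.

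The clinical analysis in section 13.6 differs: "The primary outcome will be compared between groups using logistic regression, adjusted for site and baseline dental caries". Counts, including fillings, get Poisson regression with the same two covariates. Section 13.3.1 describes the allocation: "Randomisation lists will be generated using block randomisation with random variable block length, stratified by site and age".

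**The concern.** The caries and filling outcomes that section 13.6 adjusts for site and baseline caries reappear in the economic analysis as crude differences between arms. The cost difference is crude too. The economic sections do consider covariates, but the ones they name leave out the charted measure of baseline disease and both stratification factors.

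Three things follow if those variables predict the outcome:

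- The incremental cost and effect are estimated with more variance than the data require, so the acceptability curves are flatter than they need be.
- An unstratified standard error still counts between-site variation that the stratified allocation has removed from the comparison, so it is somewhat too large.
- A chance difference between arms in baseline caries passes straight into the cost difference.

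Objective 3, the cost-effectiveness comparison, rests on these quantities.

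**Working it through.** **The plan's own figure.** Section 13.2.1 gives 363 per group for a 12-point difference, 90% power and alpha 0.05 (taken as two-sided). With n = [1.96·√(2p̄(1−p̄)) + 1.2816·√(p1(1−p1)+p2(1−p2))]² / d² and 56% versus 44%, n = (1.3859 + 0.8997)² / 0.0144 = 363. Taking 62% versus 50% gives 358. Allowing for 20% loss, 363/0.8 = 454 per group and 908 in total. The sample size is not at issue; 2 × 363 = 726 analysed children is the base for what follows.

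**Cost: gain from baseline caries.** The protocol gives neither a correlation rho between baseline caries and 24-month cost nor a power for cost, so both are assumptions. Adjustment multiplies variance by f = 1 − rho². A contrast with 80% power unadjusted has power Φ((1.96 + 0.8416)/√f − 1.96) after adjustment. If the arms differ by chance by 1.96 SE in baseline caries, the unadjusted cost difference moves by rho × 1.96 of its own SE.

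| rho | f | equivalent analysed children, 726/f | power from 80% | shift (SE) |
|---|---|---|---|---|
| 0.1 | 0.99 | 733 | 80.4% | 0.20 |
| 0.2 | 0.96 | 756 | 81.6% | 0.39 |
| 0.3 | 0.91 | 798 | 83.6% | 0.59 |
| 0.4 | 0.84 | 864 | 86.4% | 0.78 |
| 0.5 | 0.75 | 968 | 89.9% | 0.98 |

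**Site: conservatism.** If 10% of outcome variance lay between sites (assumed), a nominal 5% test that ignores the strata would have true size 2(1 − Φ(1.96/√0.90)) = 3.9%. This is separate from the gain above. Stratification already removes the site share from the true variance of the estimate, so the two should not be multiplied into one power gain.

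**Caries difference.** At 62% versus 50% with 363 per arm, SE = √((0.62·0.38 + 0.50·0.50)/363) = 0.0366, and the 95% half-width is 1.96 × 0.0366 = 7.2 points. If site and baseline caries explain a share R² of the variance (assumed), the half-width is multiplied by √(1 − R²), and the equivalent number per arm is 363/(1 − R²):

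- R² 0.05: 7.0 points, 382 per arm
- R² 0.10: 6.8 points, 403 per arm
- R² 0.20: 6.4 points, 454 per arm
- R² 0.30: 6.0 points, 519 per arm

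**Simulation check.** The set-up was 726 children and 40 sites, with allocation balanced within site and 400 replicates per setting. With nothing prognostic, the adjusted and unadjusted model SEs were equal (ratio 1.00). With site effects only, the unadjusted model SE averaged 0.0365 to 0.0366 against an observed spread of about 0.035. With 400 replicates that spread carries roughly 1/√800 = 3.5% Monte Carlo error, so this agrees with the formula but does not size the effect. With the strongest site and baseline effects tried, the model-SE ratio was about 0.86.

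**Resampling cells.** 726/(40 × 2) is about 9 children per arm-by-site cell. Bootstrapping within cells of 9 understates variance by about 1/9 = 11%, or about 6% in SE (√(8/9) = 0.943).

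**The case against.** The strongest reply is that the protocol summarises an economic plan still to be written, that covariate lists normally belong there, and that nothing here is an error. Much of this stands. Sections 13.7 and 10.8.8 name socio-economic status and ethnicity without saying that nothing else will be entered, and neither says how bootstrap resamples are drawn. The t-test and the secondary role of the regression are, however, positive statements of method, given among the main features of that plan.

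Four stronger readings are tempting but not supported:

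- **That the economic estimates are biased.** Allocation is randomised 1:1, so crude differences are unbiased, and ignoring strata makes tests conservative rather than liberal.
- **That the standard errors are certainly too large.** This holds only if site or age predicts the outcome, and the protocol gives no such figure.
- **That baseline caries must drive cost because every child enters with a dentinal lesion.** A feature shared by all children explains no variation between them. Eligibility also narrows the range, since advanced caries needing referral for extractions is excluded. A rho of 0.1 or 0.2, with almost no gain, is possible.
- **That the caries effect in the ratio ought to equal the primary estimate.** The primary model is logistic, while a cost-effectiveness ratio needs an absolute difference. Some mismatch is inherent, and a linear adjusted model would not remove it.

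The 80% starting power is also only illustrative: the protocol sets no power for cost, and acceptability curves are not 5% tests.

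**Conclusion.** The point holds as one of efficiency and consistency. The economic sections fix an unadjusted comparison as the main estimate and do not name baseline caries, site or age, while section 13.6 adjusts the same caries and filling outcomes for site and baseline caries. The gain from adjusting ranges from negligible (about 1% of variance at rho 0.1) to substantial (25% at rho 0.5), and the documents do not say where in that range the trial lies. For the caries difference the interval would narrow by about 2.5% at R² 0.05 and 16% at R² 0.30. Protection against chance imbalance in baseline caries scales with the same unknown correlation. Validity is not in question. The case for change is that the data are already collected and the covariates can be fixed before any comparative cost data are seen.

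**What to change.** In sections 13.7 and 10.8.8, and then in the economic analysis plan:

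- Take base-case incremental cost and effect from a seemingly unrelated regression with treatment, site, age and baseline caries in both equations, adding socio-economic status and ethnicity as already planned.
- Refit that model in each bootstrap resample. Draw resamples within arm, not within arm-by-site cells unless a small-cell correction is applied.
- Build the ratios and acceptability curves from the adjusted differences. Keep raw means and t-tests as description.
- Beside the caries effect in the ratio, report an adjusted marginal risk difference from the primary logistic model, and state that the two need not be identical.

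The cost is a short edit and no new data collection. The downsides are up to 40 site terms with about 726 children (a site random intercept is an alternative) and the need to fit the model and bootstrap together with the planned multiple imputation. The economic analysis plan should spell out that last step.

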# 14 DATA MANAGEMENT AND TRIAL MONITORING

For the CHOICE trial the responsibilities for Data Management and monitoring are delegated to the LCTC. Separate Data Management and Trial Monitoring Plans will provide detail regarding the internal processes that will be conducted at the LCTC throughout the trial. Justification for the level of monitoring is provided within those documents and the trial-specific risk assessment. All data will be managed as per local LCTC processes and in line with all relevant regulatory, ethical and legal obligations.

## 14.1 **Source Documents**

Source data is all information, original records of clinical findings, observations, or other activities in a clinical trial necessary for the reconstruction and evaluation of the trial. Source data are contained in source documents. Examples of these original documents, and data records include: questionnaires, hospital records, dental records, clinical and office charts, laboratory notes, memoranda, subjects' diaries or evaluation checklists, pharmacy dispensing records, recorded data from automated instruments, copies or transcriptions certified after verification as being accurate and complete, microfiches, photographic negatives, microfilm or magnetic media, x-rays, subject files, and records kept at the pharmacy and laboratory departments involved in the study.

Each participating site should maintain appropriate medical and research records for this trial, in compliance with ICH E6 GCP, Section 4.9 and regulatory and institutional requirements for the protection of confidentiality of subjects

The electronic case report form (eCRF) will be considered the source document for data where no prior record exists and which is recorded directly in the bespoke eCRF.

Date(s) of informed consent processes (including date of provision of patient information, randomisation number and the fact that the patient is participating in a clinical trial (including possible treatment arms) should be added to the patient's dental record chronologically.

## 14.2 Data Collection Methods

The study electronic case report form (eCRF) is the primary data collection instrument for the study. All data requested on the eCRF must be recorded with data being entered in a timely fashion.

Study data will be captured using remote data entry at research sites. Study staff will be trained and delegated the duty of eCRF completion. Training will be given to delegated staff at the Site Initiation Visit.

See section 12: Safety reporting for details on how to report SAEs.

Questionnaires will be completed electronically via a link sent out to parents/primary caregivers. Follow up via telephone or post may occur if questionnaires are not completed electronically.

## 14.3 Monitoring

Monitoring is conducted to ensure protection of patients participating in the trial and all aspects of the trial (procedures, trial intervention administration and data collection) are of high quality and conducted in accordance with sponsor and regulatory requirements.

A detailed Trial Monitoring Plan will be developed and agreed by the TMG and CI to describe who will conduct the monitoring, at what frequency monitoring will be done, and what level of detail monitoring will be conducted. This

will be dependent on the documented risk assessment of the trial which determines the level and type of monitoring required for specific hazards. All processes may be subject to monitoring, e.g., enrolment, consent, adherence to trial interventions, accuracy and timeliness of data collection etc.

Trial Oversight Committees related to the monitoring of the trial are detailed in Roles and Responsibilities see section 4.7.

## 14.3.1 Central Monitoring

There are a number of monitoring features in place at the LCTC to ensure reliability and validity of the trial data, to be detailed in the Trial Monitoring Plan. Data will be entered into a validated database and during data processing there will be checks for missing or unusual values (range checks) and for consistency within participants over time. Other data checks relevant to patient rights and safety will also be regularly performed as per LCTC processes. Any suspect data will be returned to the site in the form of data queries. Data queries are processed entirely through the eCRF system and must be responded to by the site team. Sites will respond to the queries providing an explanation/resolution to the discrepancies directly on to the trial database.

Site monitoring visits may be 'triggered' in response to concerns regarding study conduct, participant recruitment, outlier data or other factors as appropriate.

### 14.3.2 Clinical Site Monitoring

In order to perform their role effectively, the Trial Manager (or monitor) and persons involved in Quality Assurance and Inspection may need direct access to primary data, e.g., patient dental records, appointment books, etc. Since this affects the participant's confidentiality, this fact is included on the PISC. In agreeing to participate in this study, a PI grants permission to the Sponsor (or designee), and appropriate regulatory authorities to conduct on-site monitoring and/or auditing of all appropriate study documentation. The purposes of site monitoring visits include, but are not limited to:

- assessing compliance with the study protocol;
- discussing any emerging problems that may have been identified prior to the visit;
- checking eCRF and query completion practices.

## 14.4 Risk Assessment

In accordance with the relevant LCTC standard procedures, this trial will undergo a risk assessment, completed in partnership between:

- Sponsor representative (s)
- Chief Investigator
- LCTC workstreams

In conducting this risk assessment, the contributors consider potential participant, organisational, and study hazards, the likelihood of their occurrence and resulting impact if they should occur.

The CHOICE trial is determined to be a low risk trial.

